## Appendix 8: WHO model prescribing information for classification of topical corticosteroids

Hydrocortisone and betamethasone are examples of low- and high-potency TCS. TCS have been ranked in terms of potency into 4 groups consisting of 7 classes. Class I TCS are the most potent and Class VII TCS are the least potent ([Panel 15](#)). Efficacy and side-effects are greatest with the Class I ultra-high-potency preparations which should only be used for limited time periods (2-3 weeks).

Representative preparations by group are listed in the table below according to the WHO model prescribing information for drugs used in skin diseases (41). These groups may vary depending on the formulation and concentration and should be considered approximate. In general, ointments are more potent than creams or lotions. Potency is also increased when TCS are used under occlusive dressings or in intertriginous areas.

### Panel 15: Classification of topical corticosteroids

Potency	Class	Topical corticosteroid	Formulation
Ultra high	I	Clobetasol propionate	Cream, 0.05%
		Diflorasone diacetate	Ointment, 0.05%
High	II	Amcinonide	Ointment, 0.1%
		Betamethasone dipropionate	Ointment, 0.05%
		Desoximetasone	Cream or ointment, 0.025%
		Fluocinonide	Cream, ointment, or gel, 0.05%
		Halcinonide	Cream, 0.1%
	III	Betamethasone dipropionate	Cream, 0.05%
		Betamethasone valerate	Ointment, 0.1%
		Diflorasone diacetate	Cream, 0.05%
		Triamcinolone acetonide	Ointment, 0.1%
	Moderate	IV	Desoximetasone
Fluocinolone acetonide			Ointment, 0.025%
Fludroxycortide			Ointment, 0.05%
Hydrocortisone valerate			Ointment, 0.2%
Triamcinolone acetonide			Cream, 0.1%
V		Betamethasone dipropionate	Lotion, 0.02%
		Betamethasone valerate	Cream, 0.1%
		Fluocinolone acetonide	Cream, 0.025%
		Fludroxycortide	Cream, 0.05%
		Hydrocortisone butyrate	Cream, 0.1%

SCORAD	Scoring Atopic Dermatitis
SCORAD50	At least 50% reduction in SCORAD score
SCORAD75	At least 75% reduction in SCORAD score
SOC	system organ class

Tdap	Tetanus, diphtheria and acellular pertussis
ULN	upper limit of normal
VAS	visual analogue scale

4 Introduction

The statistical analysis will be performed as outlined in the clinical trial protocol.

This statistical analysis plan is prepared before the unblinding of the trial and supplements the clinical trial protocol, which otherwise describes the originally planned statistical analyses of all endpoints in an intended exhaustive manner. The statistical analysis plan contains a more technical and detailed elaboration of some points related to the implementation of the statistical analysis already described in the clinical trial protocol.

In addition, the Statistical Analysis Plan includes supplementary statistical analyses and aspects that are introduced after the protocol.

Definition of vaccine response:

1. The definition and calculation of positive meningococcal response has been specified.

New analysis for the continuous other endpoints:

2. Analysis of a new tertiary estimand ('composite') for the continuous other endpoint 'Change from baseline to Week 16 in EASI score' is introduced. Analysis apply non-responder imputation for subjects who receive rescue medication.
3. A repeated measurements analysis of the percentage change from baseline in EASI score from baseline to Week 16 has been added.

The per protocol analysis set:

4. The definition of the per protocol analysis set as stated in the protocol has been updated with regards to handling of systemic rescue medication, baseline disease severity related to the EASI status and visit interval between administration of the vaccine and measurement of the vaccine response.

5 Trial analysis sets

The trial analysis sets are defined in the protocol and the following modifications to the analysis sets are introduced.

All subjects randomised to treatment who were exposed to IMP (tralokinumab/placebo) are included in the full analysis set and will be analysed for efficacy up to Week 16 (Visit 11). For subjects not exposed to IMP (tralokinumab/placebo), the decision to withdraw can't be biased by knowledge of the assigned treatment due to the blinding. This definition of the full analysis set implements the consideration mentioned in the protocol regarding special excluded cases with reference to ICH E9, Section 5.2.1.

The safety analysis set comprises all subjects randomised to treatment who were exposed to IMP. The protocol further specifies to exclude subjects from the safety analysis set for whom no post-baseline safety data are available. However, since all subjects receive the first dose of IMP in connection with the Week 0 visit and are subsequently monitored for immediate drug reactions, all exposed subjects are considered to have post-baseline safety data available and no such further exclusions will be made.

In addition to the analysis sets defined in the protocol, a safety follow-up analysis set will be used as the basis for evaluation of adverse events during the safety follow-up period. It comprises all subjects for whom date of last contact is after the date of exposure end, where exposure end is defined as the Week 16 visit for subjects completing the treatment period, and otherwise the date of permanent discontinuation of IMP (tralokinumab/placebo) for subjects not completing the treatment period. See also Section 6.9.2 for further details.

For analysis of efficacy, subjects will be included 'as randomised'.

For analysis of safety, if a subject is mistakenly given an IMP other than that to which they were randomised, they will be analysed 'as treated', thus included in the group according to the therapy actually received by the subject. The below rules will be applied.

Subjects who received at least one dose of tralokinumab will be analysed in the tralokinumab treatment group. Although this may dilute the AE rate in the tralokinumab treatment group slightly by including in the denominator subjects who only received one dose of active treatment, it will ensure that no significant drug reactions to tralokinumab will erroneously be assigned to placebo.

The definition of the per protocol analysis set as described in the protocol has been updated to accept negligible deviations in baseline disease severity related to the EASI status. Thus, the criteria from inclusion criterion 7 have been modified to require an EASI score of ≥ 12 at screening OR ≥ 16 at baseline instead of requiring both criteria to be met. The rationale for this change is that marginal deviations in baseline disease severity is not considered to affect the vaccine response.

The criteria related to systemic rescue medication in the definition of the per protocol analysis set have been updated relative to the protocol text to include, not only those for the AD indication but all systemic immunosuppressive treatments irrespectively of indication. The referred criteria for excluding patients consequently become:

- Initiated systemic immunosuppressive treatment prior to Week 10 and who are still treated with or exposed to the given treatment at Week 10 (that is, Week 10 [visit 8] occurs within 5 half-lives after the last dose of the given systemic immunosuppressive medication).
- Initiated systemic immunosuppressive treatment at any time point from Week 10 to Week 16.

The rationale for excluding these subjects is to ensure that subjects were not immunosuppressed by these treatments when the vaccinations were administered, as this might impact the response to the vaccination, and thereby the primary endpoints. This is independent of the indication for the immunosuppressive treatments and should therefore include all subjects treated with systemic immunosuppressants, irrespectively of the indication.

In addition to the criteria specified in the protocol, subjects with Week 16 visit occurring ≥ 56 days after the Week 12 visit, are not included in per protocol analysis set due to a too long interval between administration of the vaccine and measurement of the vaccine response, since this would induce a risk of a perished vaccine response.

Systemic immunosuppressive treatment definition

ATC2 code H02 or L04 will be used to identify administered systemic immunosuppressive treatments. [Table 1](#) below presents the medications that as minimum will be identified in the trial (as being systemic immunosuppressive) along with the half-lives applied to evaluate the PP exclusion criteria.

Medications administered in the screening period will be included in the search to ensure that all administered medications that could potentially be immunosuppressive at time of vaccination will be covered. Different routes of administration can be used for the medications, which will result in different half-lives.

Table 1: Systemic immunosuppressive treatments and applied halflives

ATC 4	ATC 4 TERM	Standardized Medication Name	Route of Administration	Halflife		
				Hours	Weeks	5 x t _{1/2} ¹
H02AB	GLUCOCORTICOIDS	DEXAMETHASONE	ORAL	7.2	0.0	0.2

H02AB	GLUCOCORTICOIDS	DEXAMETHASONE SODIUM PHOSPHATE	INTRAVENOUS	24	0.1	0.7
H02AB	GLUCOCORTICOIDS	DEXAMETHASONE SODIUM PHOSPHATE	SUBCUTANEOUS	336	2.0	10.0
H02AB	GLUCOCORTICOIDS	HYDROCORTISONE SODIUM SUCCINATE	INTRAVENOUS	3	0.0	0.1
H02AB	GLUCOCORTICOIDS	METHYLPREDNISOLONE	ORAL	3.5	0.0	0.1
H02AB	GLUCOCORTICOIDS	METHYLPREDNISOLONE SODIUM SUCCINATE	INTRAVENOUS	24	0.1	0.7
H02AB	GLUCOCORTICOIDS	PREDNISONE	ORAL	3	0.0	0.1
H02AB	GLUCOCORTICOIDS	TRIAMCINOLONE ACETONIDE ²	INTRAMUSCULAR	336	2.0	10.0
H02AA	MINERALOCORTICOIDS	FLUDROCORTISONE ACETATE	ORAL	0.5	0.0	0.0
L04AC	INTERLEUKIN INHIBITORS	DUPILUMAB	SUBCUTANEOUS	432	2.6	12.9
L04AC	INTERLEUKIN INHIBITORS	DUPILUMAB	INTRAMUSCULAR	432	2.6	12.9
L04AC	INTERLEUKIN INHIBITORS	NEMOLIZUMAB	SUBCUTANEOUS	432	2.6	12.9
L04AX	OTHER IMMUNOSUPPRESSANTS	AZATHIOPRINE	ORAL	5	0.1	0.1
L04AX	OTHER IMMUNOSUPPRESSANTS	METHOTREXATE	ORAL	15	0.1	0.4
L04AA	SELECTIVE IMMUNOSUPPRESSANTS	BARICITINIB	ORAL	12.5	0.1	0.4
L04AA	SELECTIVE IMMUNOSUPPRESSANTS	MYCOPHENOLATE SODIUM	ORAL	17	0.1	0.5

¹ 5 times the half-life ($t_{1/2}$) is presented in weeks.

² Intralaminar and intraarticular administration of Triamcinolone Acetonide is not considered systemic treatment

Systemic immunosuppressive medications were prohibited during the trial, and wash-out criteria were specified in the exclusion criteria of the protocol accordingly. For completeness, medications that required wash-out will be included in the above search.

6 Statistical analysis

6.1 Baseline characteristics

Baseline characteristics will be summarised and listed.

Duration of AD in years will be calculated as (age at Week 0) minus (age at onset of AD).

The table of concomitant medication at baseline will include medication starting before the first dose of IMP which does not end before the first dose of IMP. For further details, see Section [6.9.3](#).

6.2 Disposition

Subject disposition will be summarised and listed.

6.3 Rescue medication

Rescue medication is defined by the following algorithm: Concomitant medications with Dermatitis atopic or Dermatitis infected as the preferred term for the indication and either ATC2 code H02 or D07, or ATC4 code D11AH, or preferred name Methotrexate, Ciclosporin, Azathioprine, Mycophenolate-mofetil, Mycophenolate-sodium, Mycophenolate-acid, or Dupilumab.

According to the protocol, investigators should make every attempt to conduct efficacy and safety assessments immediately before administering any rescue treatment. Therefore, if rescue medication has start date the same day as an efficacy assessment, then the assumption will be that the assessment is not influenced by the rescue medication.

The table of rescue medication will include medications taken after the first dose and before the Week 16 visit (or before day $7 \times 16 = 112$ after first dose, in case the Week 16 visit did not take place).

Rescue medication will be summarised for the treatment period. In addition, a summary table of rescue medication by type (topical and systemic) and by overall group (corticosteroids, immunosuppressants, and other) will be made.

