#### **9.5 Rescue treatment**

If medically necessary (i.e., to control intolerable AD symptoms), rescue treatment for AD may be provided to trial subjects at the discretion of the investigator.

If possible, investigators should attempt to limit the first step of rescue therapy to topical medications, and escalate to systemic medications only for subjects who do not respond adequately after at least 14 days of topical treatment.

Subjects who receive topical rescue treatment (TCS of any WHO class [see [Appendix 8](#)], or TCI) will continue treatment with IMP (tralokinumab/placebo) and will receive the vaccines. TCI may be used for rescue, but should be reserved for body areas where TCS is not advisable or on areas where continued treatment with TCS is considered unsafe.

If a subject receives rescue treatment with systemic corticosteroids or non-steroidal systemic immunosuppressive drugs (cyclosporine, methotrexate, mycophenolate mofetil, azathioprine, etc.), IMP will be immediately discontinued (see Section [10.2.2](#), reasons for temporary discontinuation of IMP). After the treatment with these medications is completed, IMP may

be resumed if deemed appropriate by the investigator and sponsor's medical expert, but not sooner than 5 half-lives after the last dose of systemic rescue medication.

Investigators should make every attempt to conduct efficacy and safety assessments (for example disease severity scores [IGA and EASI], safety labs) immediately before administering any rescue treatment. An unscheduled visit may be used for this purpose, if necessary.

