## 9.6 Concomitant medication and concurrent procedures

Any medication or vaccine that the subject receives from 3 months prior to screening through safety follow-up (Week 30) must be recorded in the subject's medical record and the eCRF along with details such as:

- Medication name.
- Indication.
- Start and stop date of administration (it will also be recorded if the medication is ongoing).
- Dosage information, including dose per administration, unit, and frequency.
- Route of administration.
- Dose form (cream, lotion, ointment, other); this is only required for topical treatments.

Similarly, concurrent procedures must also be recorded in the subject's medical record and the eCRF. The following data will be recorded: name of procedure, indication, body location (upper limb, lower limb, trunk, head), and start and stop date. Note: in this trial, only surgical procedures and procedures related to AD treatment (e.g., phototherapy or bleach baths) will be recorded.

Investigators may prescribe concomitant medications or treatments to provide adequate supportive care as deemed necessary, except for medications listed in Section 9.7. The sponsor's medical expert should be contacted if there are any questions regarding concomitant or prior therapy.

Concomitant medication for conditions other than AD may be continued throughout the trial without any change in dosage whenever possible.

The following concomitant medications related to AD treatment are permitted from screening through safety follow-up (Week 30):

- Oral antibiotics, antiviral, or antifungal therapy for skin infections as appropriate.
- Stable doses of an emollient (subjects must apply such emollients twice daily [or more, as needed] for at least 14 days before baseline and throughout trial participation).
- Oral anti-histamines.

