**Panel 6: Prohibited medication**

Medication	Prohibited from	Prohibited to	Temporary discontinuation of IMP required
Topical medications used for treatment of AD, including: 
 
• TCS of any WHO class.
 
• TCI.
 
• PDE-4 inhibitors.
 
	Week -2 (2 weeks prior to randomisation)	Week 16 (end of treatment)	No
Use of UVA or UVB, psoralen + UVA (PUVA), other phototherapy, or tanning beds.	Week -6 (6 weeks prior to randomisation)	Week 16 (end of treatment)	No
Three or more bleach baths per week.	Week -4 (4 weeks prior to randomisation)	Week 16 (end of treatment)	No
Investigational agents other than tralokinumab.	3 months or 5 half-lives  prior to randomisation	Week 30 (safety follow-up)	Yes
Immunoglobulin.	3 months or 5 half-lives  prior to randomisation	Week 30 (safety follow-up)	Yes
Blood products.	4 weeks prior to screening	Week 30 (safety follow-up)	Yes
Systemic corticosteroids 	Week -4 (4 weeks prior to randomisation)	Week 30 (safety follow-up)	Yes
Systemic treatment for AD with an immunosuppressive or immunomodulating agent  .	Week -4 (4 weeks prior to randomisation)	Week 30 (safety follow-up)	Yes
Allergen immunotherapy.	Randomisation	Week 30 (safety follow-up)	Yes
Vaccination of any kind (except influenza virus vaccines).	3 months prior to screening	Week 30 (safety follow-up)	Yes

1) Whichever is longer. For cell-depleting agents, the use is disallowed within 6 months of randomisation.

2) Note: nasal and inhaled corticosteroids are allowed.

3) Examples include cyclosporine, mycophenolate mofetil, azathioprine, methotrexate, Janus kinase inhibitors, interferon-gamma, dupilumab, and other biologics.

AD, atopic dermatitis; IMP, investigational medicinal product; PDE-4, phosphodiesterase 4; TCI, topical calcineurin inhibitor; TCS, topical corticosteroid; UV, ultraviolet; WHO, World Health Organization.

In case any prohibited treatments are used during the trial, they must be recorded as concomitant medication.

Refer to Section 9.5 for principles for use of rescue treatment and re-initiation of IMP after discontinuation of prohibited systemic rescue treatment.

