### 14.3.6.2 Primary estimand: ‘composite’

The primary estimand for the first 2 secondary endpoints will be:

- Treatment difference in response rates of IGA 0/1 and EASI75 after 16 weeks achieved without rescue medication, regardless of treatment discontinuation.

The primary estimand assesses the expected difference in response rates (defined as response obtained without initiation of any rescue medication) after 16 weeks, resulting from initiation of a treatment regimen with tralokinumab compared to a treatment regimen with placebo.

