#### Primary analysis for the primary estimand

Data retrieved at Week 16 for subjects who have permanently discontinued IMP prior to Week 16 will be included in the analysis. Subjects who prior to the Week 16 visit have received rescue medication will be considered non-responders, reflecting an assumption that initiation of rescue medication indicates failure of the randomised treatment to achieve response, and that a (possible) observed positive response after initiation of rescue medication is not attributable to the randomised treatment. Missing data for subjects who did not attend the Week 16 visit and where rescue medication has not been used prior to Week 16, will be imputed as non-responders.

The difference in response rates between treatment groups will be analysed using the Cochran-Mantel-Haenszel test stratified by baseline disease severity (IGA 3 or 4). The treatment estimate and the corresponding 95% CI will be presented. The null hypothesis of no difference in response rates between tralokinumab and placebo will be tested against the 2-sided alternative that there is a difference.

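### Phototherapy given for AD before Week 16 is not treated as rescue, so a subject who responds on it counts as a rescue-free responder

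*SAP*

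**What the plan says.** **Estimand.** Protocol 14.3.6.2 defines the primary estimand for the two secondary efficacy endpoints as "Treatment difference in response rates of IGA 0/1 and EASI75 after 16 weeks achieved without rescue medication, regardless of treatment discontinuation". Users of rescue before Week 16 become non-responders. One of the two reasons given is that "a (possible) observed positive response after initiation of rescue medication is not attributable to the randomised treatment".

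**What counts as rescue.** Protocol 9.5 describes topical drugs first (TCS or TCI), then systemic ones. The systemic step begins "If a subject receives rescue treatment with systemic corticosteroids or non-steroidal systemic immunosuppressive drugs" and leads to IMP being stopped. SAP 6.3 puts this into practice: "Rescue medication is defined by the following algorithm: Concomitant medications with Dermatitis atopic or Dermatitis infected as the preferred term for the indication", combined with ATC2 code H02 or D07, ATC4 code D11AH, or one of seven named drugs.

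**How phototherapy is treated.** It appears in Panel 6 of the protocol as "Use of UVA or UVB, psoralen + UVA (PUVA), other phototherapy, or tanning beds", prohibited to Week 16 with no interruption of IMP required. Section 9.6 makes it a concurrent procedure: "only surgical procedures and procedures related to AD treatment (e.g., phototherapy or bleach baths) will be recorded". Section 9.7 adds: "In case any prohibited treatments are used during the trial, they must be recorded as concomitant medication".

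**The concern.** Phototherapy is an active AD treatment. The protocol's argument for discounting a response after rescue, that the response can no longer be credited to the randomised treatment, applies equally when the added treatment is phototherapy given for AD. Yet neither document assigns this event any handling.

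Three groups of analyses are exposed:

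- the composite analysis of IGA 0/1 and EASI75, and of EASI50, EASI90, SCORAD50 and SCORAD75, which use the same method;
- the hypothetical-estimand and repeated-measures analyses, where data after phototherapy would be kept although data after rescue are dropped;
- the SAP's composite analysis of EASI change, where the Week 16 value would not be replaced by the worst observation.

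IGA 0/1 and EASI75 are in the confirmatory testing hierarchy, so their responder definition should be fixed before treatment codes are known. The direction of any error depends on the arm: mostly placebo use understates the treatment difference, and mostly tralokinumab use overstates it.

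**Working it through.** **Step 1. Trace the rule for a phototherapy-only subject.**

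- Recorded as a procedure (protocol 9.6): SAP 6.3 searches concomitant medications only, so the record is not seen.
- Recorded as a medication (protocol 9.7): the AD indication matches, but the entry has no H02, D07 or D11AH code and is none of the seven drugs, so it is not flagged.
- For comparison, a TCS record with an AD indication (D07) is flagged.

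**Step 2. Look for another rule that catches the case.**

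- Sensitivity analysis 1 changes only subjects who permanently stopped IMP.
- Sensitivity analysis 2 changes only missing Week 16 data.
- The per protocol exclusions (protocol 14.2, SAP 5) do not name phototherapy. The SAP drug search covers ATC H02 and L04.
- SAP 6.9.6 summarises and lists major deviations and does not alter responder status.

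None applies.

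**Step 3. Reproduce the plan's power figures (protocol 14.1).** Inputs: 80 per arm in the per protocol set, 80% vaccine response in both arms, margin 25 points; 100 per arm in the FAS, IGA 0/1 30% vs 10%, EASI75 40% vs 15%; one-sided 2.5%.

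- Non-inferiority: SE = √(2 × 0.8 × 0.2 / 80) = 0.0632; power = Φ(0.25/0.0632 − 1.96) = 97.7% (stated 98%).
- Superiority: power = Φ[(d − 1.96·√(2p̄(1−p̄)/n)) / √(p₁(1−p₁)/n + p₂(1−p₂)/n)]. IGA 0/1: (0.20 − 0.1109)/0.0548 gives 94.8%. EASI75: (0.25 − 0.1238)/0.0606 gives 98.1%.
- All four: 0.977 × 0.977 × 0.948 × 0.981 = 88.8% (stated about 89%).

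The planning rates are therefore a sound base for illustration.

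**Step 4. Effect of reclassifying cases.** The counts are assumed, because the documents give none. The test is Cochran-Mantel-Haenszel with one stratum and 100 per arm. With a tralokinumab responders and m responders in total:

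X² = (a − m/2)² / V, where V = 100 × 100 × m × (200 − m) / (200² × 199).

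Example, 30 vs 10: a = 30, m = 40, V = 8.04, X² = 100/8.04 = 12.44, two-sided p = 0.00042.

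| Cases moved to non-response | IGA 0/1 | Difference (points) | p | EASI75 | Difference (points) | p |
|---|---|---|---|---|---|---|
| None | 30 vs 10 | 20 | 0.00042 | 40 vs 15 | 25 | 0.00008 |
| 1 tralokinumab | 29 vs 10 | 19 | 0.00072 | 39 vs 15 | 24 | 0.00014 |
| 1 placebo | 30 vs 9 | 21 | 0.00019 | 40 vs 14 | 26 | 0.00004 |
| 3 tralokinumab | 27 vs 10 | 17 | 0.0020 | 37 vs 15 | 22 | 0.0004 |
| 3 placebo | 30 vs 7 | 23 | 0.00003 | 40 vs 12 | 28 | 0.000007 |

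**Step 5. Tipping point.** For IGA 0/1, 20 vs 10 gives p = 0.048 and 19 vs 10 gives p = 0.071, so 30 − 19 = 11 tralokinumab responders must move. For EASI75, 27 vs 15 gives p = 0.038 and 26 vs 15 gives p = 0.055, so 40 − 26 = 14 must move.

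**The case against.** The strongest reply is that the estimand is defined and followed. The intercurrent event is rescue medication, 9.5 describes it as drugs, and SAP 6.3 searches for drugs. Whether a prohibited procedure should also count as failure is then a choice of scope. This stands to the extent that the SAP does not depart from the protocol. It does not explain why a response on another active AD therapy should be reported as achieved without rescue.

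A second reply is that phototherapy is a deviation, not planned rescue. But the Panel 6 row "Topical medications used for treatment of AD, including" TCS and TCI has the same status: prohibited to Week 16, IMP not stopped. The real difference is that 9.5 goes on to allow those topicals as rescue and never mentions phototherapy. That separates planned from unplanned use, but not whether the later response belongs to the randomised treatment.

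A third reply is that the protocol also justifies the non-responder rule by treating rescue as a sign of treatment failure, which need not fit every use of phototherapy. Restricting the rule to use with an AD indication largely meets this.

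Two points remain. Frequent bleach baths have the same Panel 6 status and are also recorded as AD procedures; the proposal does not settle them, though this does not make the phototherapy rule unsound. And several conditions must coincide: phototherapy for AD, no listed drug although topicals are the preferred first step, IMP continued, Week 16 attended and the threshold met. Many phototherapy users may already be flagged through topical rescue.

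**Conclusion.** The concern holds as a minor one. As written, AD phototherapy is missed by either recording route, and no other rule changes the subject's status. The size rests on assumed counts, the planning response rates, 100 per arm and a single stratum. On that basis three cases in one arm shift a difference by 3 points and leave every p-value at about 0.002 or below, and a reversal would need an implausible number of cases for a prohibited procedure. The treatment-policy estimand is untouched because it disregards rescue by definition.

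**What to change.** Extend SAP 6.3 before the randomisation code is broken, using the blinded review described in protocol 14.3.10. Phototherapy (UVA, UVB, PUVA or other) with an AD indication, found in procedure or medication records and starting after first dose and before the Week 16 visit, is handled as rescue:

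- non-response in the composite analyses of the binary endpoints, and worst observation carried forward for EASI change;
- data after its start not used in the hypothetical-estimand and repeated-measures analyses;
- no change to the treatment-policy estimand.

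The SAP is signed, and the documents do not show whether the code has since been broken. If it has, the same rule can be reported as an additional analysis labelled as such.

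The cost is one or two sentences and one programming step. Section 9.6 already collects the indication and the start and stop dates. A few subjects may become non-responders; if there are no cases, nothing changes.

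### SAP 6.3 counts a drug as rescue only if its indication codes to one of two terms, with no stated review of other records, so topical rescue for AD coded elsewhere can pass as unaided IGA 0/1 or EASI75 response

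*SAP*

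**What the plan says.** **Protocol.** Section 9.5 ties rescue to its purpose: "If medically necessary (i.e., to control intolerable AD symptoms), rescue treatment for AD may be provided to trial subjects". It names the drug classes: TCS of any WHO class or TCI as topical rescue, and "rescue treatment with systemic corticosteroids or non-steroidal systemic immunosuppressive drugs". Section 9.6 lists AD-related medication that is allowed and is not called rescue: oral anti-infectives for skin infection, emollient and oral anti-histamines. It also lists what sites record for each drug. An indication is on that list; a rescue flag is not.

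Section 14.3.6.2 defines the composite estimand for IGA 0/1 and EASI75 by "response obtained without initiation of any rescue medication", and its primary analysis states: "Subjects who prior to the Week 16 visit have received rescue medication will be considered non-responders". Neither statement depends on how an indication is coded.

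**SAP.** Section 6.3 defines rescue by an algorithm with two conditions, both required. The indication condition is "Concomitant medications with Dermatitis atopic or Dermatitis infected as the preferred term for the indication". The drug condition begins "and either ATC2 code H02 or D07, or ATC4 code D11AH, or preferred name Methotrexate" and continues with other named systemic drugs. The section describes no review of records that meet the drug condition but carry another indication term.

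**The concern.** The protocol asks whether the drug was used for AD. The SAP asks whether the coded indication is one of two terms. The answers agree only if every relevant record codes to Dermatitis atopic or Dermatitis infected. Because the protocol describes rescue as control of AD symptoms, a site could plausibly record a symptom or a general eczema or dermatitis term for a TCS started during an AD flare. If that entry codes to a third term, the algorithm passes over the record.

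The flag is used in several analyses:

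- the composite estimand for IGA 0/1 and EASI75, both in the formal testing hierarchy;
- EASI50, EASI90, SCORAD50 and SCORAD75, which follow the same analysis;
- the hypothetical estimand and the repeated-measures models, which are meant to drop data collected after rescue and would keep it for a missed user;
- the composite analysis of change in EASI added in SAP 6.7.

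The treatment-policy estimand disregards rescue by design, and the vaccine primary endpoints do not use this flag.

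**Working it through.** **1. Can another passage catch a missed record?** The Protocol 9.6 fields contain no rescue flag, and SAP 6.3 has no review step. Panel 6 prohibits TCS and TCI for AD up to Week 16 but does not require IMP to be interrupted, so a missed topical user leaves no trace through dosing. SAP section 5 drops the indication condition, but only for systemic immunosuppressants and only for the per protocol set. I found nothing that closes the gap for topical use.

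**2. Reproduce the plan's power (Protocol 14.1).** Inputs: 100 per arm in the FAS, 80 per arm per protocol, IGA 0/1 30% vs 10%, EASI75 40% vs 15%, vaccine response 80% in both arms with margin -25%, one-sided 2.5%.

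- Superiority power = Φ{[d − 1.96·√(2p̄(1−p̄)/n)] / √([p₁(1−p₁)+p₂(1−p₂)]/n)}, where d is the difference and p̄ the mean of the two rates.
- IGA 0/1: (0.20 − 1.96×0.0566)/0.0548 = 1.63, power 94.8%. EASI75: 98.1%.
- Non-inferiority: Φ{0.25/√(2×0.8×0.2/80) − 1.96} = 97.7% (stated: 98%).
- All four, assuming independence: 0.977² × 0.948 × 0.981 = 88.8% (stated: about 89%).

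The stated figures reproduce and are not in dispute.

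**3. Effect of missed rescue.** Each arm's response rate rises by r × m × q, where r is the share using topical rescue, m the share of users whose records all code elsewhere, and q the share of those who meet the threshold. The documents give none of these three, so every value below is an assumption.

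| r (tralokinumab / placebo) | m | q | IGA 0/1 rates | Difference | IGA 0/1 power | EASI75 power |
|---|---|---|---|---|---|---|
| none missed | – | – | 30.0% vs 10.0% | 20.0 | 94.8% | 98.1% |
| 10% / 20% | 10% | 30% | 30.3% vs 10.6% | 19.7 | 93.8% | 97.8% |
| 20% / 40% | 20% | 30% | 31.2% vs 12.4% | 18.8 | 90.2% | 96.4% |
| 20% / 20% | 25% | 40% | 32.0% vs 12.0% | 20.0 | 93.3% | 97.7% |
| 20% / 40% | 25% | 40% | 32.0% vs 14.0% | 18.0 | 86.2% | 94.8% |
| 20% / 40% | 50% | 40% | 34.0% vs 18.0% | 16.0 | 73.6% | 88.8% |

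Example, third row: placebo 0.40 × 0.20 × 0.30 = 2.4 points; tralokinumab 0.20 × 0.20 × 0.30 = 1.2 points; difference 20.0 − 2.4 + 1.2 = 18.8 points.

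**4. Direction.** With equal rescue the difference stays at 20 points, both rates are too high, and power drops slightly because the variance grows. If the 20%/40% rescue shares are reversed (m 25%, q 40%), the rates are 34% vs 12% and the difference widens to 22 points. The direction therefore follows from the assumed balance of missed responders between arms; the documents do not supply it.

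**The case against.** **An AD-indication condition agrees with the protocol.** This stands. Protocol 9.5 speaks of rescue for AD, and Panel 6 likewise prohibits topical products used to treat AD. A reader might infer that the protocol counts any treatment of intolerable AD symptoms as rescue. It does not: 9.5 names the drug classes, and 9.6 permits oral anti-histamines, emollient and oral anti-infectives. What remains is the restriction to two coded terms without a check on the others.

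**The documents do not show how indications are coded.** This also stands. No dictionary or convention for indications is given; the MedDRA statement in Protocol 14.3.8.1 concerns AEs. It cannot be said from the documents that entries such as eczema or itch code elsewhere, only that the algorithm excludes them if they do.

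**The two terms may already reflect blinded data review.** Protocol 14.3.10 requires the analyses to be reviewed against blinded data before the SAP is final, and the specific drug and route entries in SAP Table 1 suggest that recorded medication informed the plan. That is possible, but SAP 6.3 does not say that topical records with other indications were examined.

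**General data controls could help.** Worsening of AD is reportable as an AE, sites can be queried, and data quality meetings are planned. These may improve the entries, but none reclassifies a record that the algorithm has passed over.

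**The size is assumed, and any bias would be conservative.** The first half stands: every rate is assumed, and a 30% response among missed placebo users is three times the planned placebo rate. The second half holds only if missed responders are more frequent on placebo, as step 4 shows.

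**Conclusion.** The gap in the text is real. Taken literally, SAP 6.3 can score a subject who used a TCS or TCI for AD as a responder without rescue, contrary to Protocol 14.3.6.2, and can keep that subject's post-rescue data in analyses meant to exclude it.

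The number affected is unknown and may be zero. In any arm with a missed responder, the rate of response without rescue is overstated. The treatment difference shrinks only if such subjects are more frequent on placebo. With placebo rescue set at twice the tralokinumab rate, 10-20% of users missed and 30% of those responding, IGA 0/1 power falls from about 95% to 90-94%, and EASI75 loses under 2 points. The harsher rows (86% and 74% for IGA 0/1) need 25-50% of users missed and 40% of them responding, and nothing in the documents makes those values likely.

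A reader might infer a demonstrated loss of power, or a bias against tralokinumab. The documents support neither, because both depend on assumed rates. The point is worth correcting because it touches two hierarchically tested endpoints and the remedy is cheap. It does not threaten the primary objective.

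**What to change.** In SAP 6.3, keep the AD-indication condition and add a step before unblinding. List every D07 and D11AH record started after first dose and before the Week 16 assessment whose indication carries any other term. Have the list reviewed blinded to treatment, classify as rescue the records judged to be for AD, and document each decision.

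Add one sensitivity analysis of IGA 0/1 and EASI75 that counts all D07 and D11AH use in that window as rescue, whatever the indication.

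Do not simply add symptom terms such as pruritus, rash or erythema to the algorithm without review. Subjects receive repeated subcutaneous injections and two vaccinations at Week 12. A topical steroid for a reaction to one of these would then make the subject a non-responder, and unequally by arm if reactions differ.

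The cost is one blinded listing review, a short SAP addition, one extra analysis and some judgement on ambiguous records. If the listing is empty, no result changes and the completeness of the algorithm is on record.
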